The evaluation of in utero MR needs also to include patient views about the acceptability of MR imaging for informing their understanding of fetal anomaly. New technologies in fetal medicine raise ethical and social dilemmas for the patients involved. The views of such women and their partners are important when considering issues of clinical implementation [17]. Data from studies of MR experience outwith pregnancy suggest that this technology may be perceived positively in terms of e.g. comfort and impact on care [18]; however, it can also be associated with anxiety [19, 20] and may be evaluated as less acceptable than ultrasound [21]. Overall satisfaction with prenatal diagnosis is high [22]; key factors that impact on satisfaction include participation in decision making [23], staff attitudes [23, 24] and the amount of information provided [24]. The limited data available on the use of in utero MR imaging suggest that it may generate additional distress (especially where fetal prognosis is poor [25, 26]) and more anxiety than ultrasound [27].

The research undertaken in this study is therefore a logical extension of our previous work. It will come from a large, widely representative population group and should provide definitive data on diagnostic accuracy, diagnostic confidence, effect on management and acceptability of in utero MR in a timely fashion. The study is observational, however the results of in utero MR imaging will be available to fetal medicine clinicians during the study and may therefore influence clinical management decisions in individual cases (according to clinical judgement). This scenario is already considered acceptable clinical practice in previous and ongoing research studies both within our site and in other national and international centres. Any change in clinical management and decision making directly attributable to the information provided by in utero MR imaging will be recorded prospectively, and the accuracy of that information will be compared against a postnatal or post mortem reference diagnosis.

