In addition to the patient and public involvement outlined above, which has guided the design of this protocol, the study will be conducted in compliance with the principles of Good Clinical Practice (GCP) and relevant research governance regulatory requirements.

2. Aims and objectives

The aim of the research is to assess magnetic resonance (MR) imaging as a technology to aid the prenatal diagnosis of fetal developmental brain abnormalities.

- 1) We will assess diagnostic accuracy of in utero MR compared to antenatal US through:
 - a) Measurement of diagnostic accuracy of antenatal US alone (i.e. prior to in utero MR) relative to a reference diagnosis (post-natal imaging or post-mortem examination).
 - b) Measurement of diagnostic accuracy of in utero MR (following antenatal US) relative to a reference diagnosis (post-natal imaging or post-mortem examination).
- 2) We will assess the clinical effectiveness of in utero MR through:
 - a) Change in clinical diagnostic confidence before and after an MR scan
 - b) Effect of in utero MR on prenatal counselling and management intent
- 3) Through quantitative and qualitative psychosocial measures we will assess the acceptability of the clinical care package with the use of MR imaging included.
- 4) A health economics analysis will be performed to assess whether the use of MR scans are cost effective.

Primary Hypothesis

Null

The diagnostic accuracy achieved by in utero magnetic resonance (MR) imaging following detailed ante-natal ultrasound examination for suspected developmental brain abnormalities is no greater than that achieved by ultrasound alone.

Alternative

The diagnostic accuracy achieved by in utero magnetic resonance (MR) imaging following detailed ante-natal ultrasound examination for suspected developmental brain abnormalities is greater than that achieved by ultrasound alone.

Secondary Alternative Hypotheses

Information provided by in utero MR makes a clinically effective contribution to prenatal counselling and management.

Parents view in utero MR as a useful and constructive event in their clinical pathway.

Referring fetal medicine experts believe that the images and information from in utero MR examination make a positive contribution to prenatal clinical management.

[figure not shown]
In utero MR makes a cost effective contribution to the prenatal diagnosis and management of suspected developmental brain abnormalities.

3. Study Design

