Multi-centre prospective observational study of diagnosis, management and outcome in a large cohort of pregnancies affected by abnormal fetal brain development.

The study is designed to include all developmental brain abnormalities identified by ante-natal ultrasound screening from 18 weeks gestation onwards. Participants are recruited from at least 13 sites within the UK incorporating a wide geographic and socioeconomic base. MR scanning is then carried out either in a primary unit (Sheffield) or in one of five secondary units (Newcastle, Leeds, Birmingham, Belfast and Manchester). Figure 1 outlines the study design and length of time that each participant may remain in the study process.

Figure 1. MERIDIAN study design

Primary Outcomes

- 1) Absolute diagnostic accuracy of MR as assessed by percentage of cases where in utero MR diagnosis agrees with post-mortem autopsy/MR or postnatal imaging.
- 2) Absolute diagnostic accuracy of US as assessed by percentage of cases where US diagnosis at the time of referral for MR agrees with post-mortem autopsy/MR or postnatal imaging.

Agreement between prenatal diagnosis (both before and after MR) and outcome diagnosis will be judged by an appointed independent expert panel consisting of a fetal medicine clinician, paediatric neuroradiologist and paediatric neurologist or neurosurgeon.

Secondary Outcomes

Effect of including MR scan on diagnostic confidence

Change in diagnostic confidence will be measured before and after the MR scan as assessed by a 5 point Likert scale.

Effect of including MR scan on prognosis

Change in prognosis will be measured before and after the MR scan as assessed by a 4 point categorical scale (poor – less than 50% chance of normal neuro-developmental outcome, intermediate - 50-90% chance of normal outcome, favourable - greater than 90% chance of normal outcome, normal – no abnormality found after detailed fetal medicine investigation).

Effect of including MR scan on management

Change in management will be measured before and after the MR scan as assessed by a 2 point categorical scale. This scale will record whether termination of pregnancy was discussed on the basis of poor neuro-developmental prognosis.

4. Ancillary sub-studies

Sociological Study

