The principal sensitivity analysis will examine the possible impact of repeat ultrasound, prior to possible MRI, on costs and outcomes. The likely impact of repeat ultrasound will be estimated based on the original ultrasound diagnosis, the information about the true status of the fetus obtained within the study, and combined with the existing literature and clinical expert opinion. Further sensitivity analyses will consider how travel costs may be reduced if MRI is offered at centres closer to parents' homes. This will be approximated by calculating the reduction in distance to hospital given other configurations of services, and reducing travel costs proportionately.

Finally, we will perform value of information analyses in order to identify those areas of uncertainty that may warrant further investigation.

Lost to Follow-Up

Where contact with a participant has not been successfully maintained during the study, she will be considered "lost to follow up" after one final attempted contact by telephone at 6 months following delivery (for livebirths only). This contact will only be attempted if it has not been possible to locate the necessary medical, maternity or paediatric records required for outcome data collection (in particular the outcome reference diagnosis which is drawn from postnatal imaging results). If this contact is required it will be made by the fetal medicine clinician or a midwife who has been involved with the participant's recent/ongoing clinical care. In cases of termination of pregnancy, fetal demise or perinatal death, post mortem examination results will be sought from medical records. If, for any reason, the results of a post mortem examination cannot be located within 6 months of the examination being completed, this case will be considered "lost to follow up". No further attempt will be made to contact the participant under these circumstances.

Wherever an outcome reference diagnosis is not available at the end of the 6 month period of follow up, all such cases will be retained in the study analysis of changes in fetal prognosis and management, but it will not be possible to include them in the analysis of diagnostic accuracy.

Study Safety

The following section outlines the methods for ensuring and assessing participant safety:

Definitions:

Adverse Event (AE): Any untoward medical occurrence in a subject.

Serious Adverse Event (SAE): Any adverse event such that it:

- results in death

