The assumption made in arriving at this sample size is that ultrasound achieves an accurate and complete diagnosis of a developmental brain abnormality in around 70% of cases [44-58], and with the addition of in utero MR, this figure would rise to at least 80%. If the "true" increase is just 10%, then a sample size of 336 would mean we can be sure of detecting an improvement in diagnostic accuracy with 90% power and 95% confidence. We believe that a change of this magnitude would be of clinical importance, as it could very well lead to changes in fetal prognosis and management intent in around 5% of all cases. The proposed sample size is sufficient to detect such changes in these important secondary outcome measures.

We will recruit from at least 13 fetal medicine units in England and Scotland, many of which have previously collaborated with the Sheffield in utero MR group. These centres cover a potential referral base of approximately 298,000 deliveries annually, this being around 40% of all deliveries in Great Britain. The incidence of developmental brain abnormalities detected by second trimester ultrasound screening, and therefore potentially eligible for inclusion in the study, is estimated at 3 per 1,000 deliveries [54, 58-60]. In order to recruit the required total of 750 cases, and allowing for a failure/refusal to recruit 50-60% of these eligible cases, the study will need to recruit for twenty two months.

Losses to follow-up during the study are estimated at just 10%. This figure reflects the nature of the study, as we are dealing with relatively young, healthy adults who have expressed a wish to gather more information about their pregnancy. The rate of incomplete cases, i.e. those where an outcome reference diagnosis is not achieved, is estimated at

around 20%. In support of this estimate, data from a tertiary fetal medicine department within our group indicates that their completion rate for autopsy following termination of pregnancy for fetal ventriculomegaly is 83% [58]. Allowance is also made for a small number (4%) of cancelled, abandoned or incomplete MR examinations. See Figure 3 below for estimated recruitment numbers and drop out rate at each stage of the study.

Figure 3 – Recruitment & Drop Out Estimates

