If losses to follow up are very high we will inform the fetal medicine experts who would be able to influence recruitment and retention. We will also use interim data in order to assess the chances of a successful outcome with the required sample size. If the sample size seems too low then we will make a decision whether to stop the study or to request further funding.

An interim analysis is planned after approximately 100 reference diagnoses have been obtained. This will be undertaken to assess two of the assumptions, namely that the accuracy of ultrasound is around 70% and that about two-thirds of babies will have a reference diagnosis.

Data analysis

Primary Analysis

The primary outcome analysis will report diagnostic accuracy within 95% confidence intervals. McNemar's test will be used to assess significant difference between diagnostic accuracy, with and without MR. In addition there will be conditional logistic regression analysis to look at effect modifiers such as gestational age and the nature of the suspected brain abnormality (e.g. ventriculomegaly, posterior fossa abnormalities and abnormalities of the corpus callosum).

Secondary Analyses

Analysis of the change in diagnostic confidence will use the Wilcoxon signed rank test. The effect on prognosis will be presented as a simple percentage (with 95% confidence interval) of cases where the prognostic category was changed.

Change in management will be analysed using McNemar's test.

Finally, a score-based weighted average analysis will be employed, as described by Ng and Palmer [61], which combines changes in diagnostic accuracy, diagnostic confidence and management to provide a summary measure of the clinical impact attributable to in utero MR.

Sub-group Analyses

Both singleton and multi-fetal pregnancies will be included in the primary analysis of diagnostic accuracy, however because of the specific complexities of prognosis and management in multi-fetal pregnancies these cases will be analysed as a distinct sub-group in these respects.

Missing Data

Patterns in missing data will be analysed using conditional logistic regression.

Further details of the proposed analyses are specified within the MERIDIAN Statistical Analysis Plan (see Appendix).

10. Study supervision

Three committees are being established to govern the conduct of the study:

1. Trial Management Group (TMG)
2. Trial Steering Committee (TSC)
3. Data Monitoring and Ethics Committee (DMEC)

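### The prognosis outcome counts how often the category changed, not which way it moved or whether the reference diagnosis supported the move, so it measures revision and not improvement

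*Protocol*

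**What the plan says.** Protocol Section 3 (Secondary Outcomes) defines the outcome: "Change in prognosis will be measured before and after the MR scan as assessed by a 4 point categorical scale". The categories run from poor through intermediate and favourable to normal, so they are ordered. The referral form records prognosis before MR, and the clinician's feedback form records the effect of MR on it (Section 8).

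Section 9 (Secondary Analyses) then sets the summary: "The effect on prognosis will be presented as a simple percentage (with 95% confidence interval) of cases where the prognostic category was changed". In the same section diagnostic confidence gets a Wilcoxon signed rank test, and for management, "Change in management will be analysed using McNemar's test". The weighted summary score "combines changes in diagnostic accuracy, diagnostic confidence and management"; prognosis is not a component.

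For cases without a reference diagnosis, Section 8 (Lost to Follow-Up) says "all such cases will be retained in the study analysis of changes in fetal prognosis and management". The prognosis analysis is therefore built to run without the reference.

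Section 2 states the hypothesis that these outcomes serve: "Information provided by in utero MR makes a clinically effective contribution to prenatal counselling and management". Section 9 (Sample size) expects prognosis and management intent to change in about 5% of cases and adds: "The proposed sample size is sufficient to detect such changes in these important secondary outcome measures".

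**The concern.** A revision from favourable to poor that followed a correct MR and one that followed an incorrect MR each add one case to the numerator. So does a revision in the opposite direction. The percentage cannot be negative, and it cannot distinguish a useful MR from one that unsettles prognoses at random.

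The Protocol itself treats direction and correctness as important. Section 8 (Study Safety) describes a prognosis wrongly worsened by MR and one wrongly improved by it, and regards both as clinically important. The Introduction says of changes in management and decision making attributed to MR that "the accuracy of that information will be compared against a postnatal or post mortem reference diagnosis". The prognosis analysis makes no such link.

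What is at stake is interpretation. A figure labelled as the effect of MR on prognosis, reported beside a hypothesis about effective contribution, is easily read as benefit when it measures only frequency of revision.

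**Working it through.** **Inputs.** From Section 9: 750 recruited, 4% failed MR examinations, 10% lost to follow-up, 20% without a reference diagnosis, and about 5% expected to change prognosis. The right/wrong splits below are illustrative; the Protocol gives none.

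**1. The plan's own case numbers.** 750 × 0.96 = 720 with a completed MR. 720 × (1 − 0.10 − 0.20) = 504 completed cases, matching the stated 504. Because cases without a reference stay in the prognosis analysis, its denominator could lie between 504 and about 720.

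**2. The planned statistic at the plan's own 5%.** Exact (Clopper-Pearson) 95% intervals:
- 25/504 = 5.0%, 3.2 to 7.2
- 36/720 = 5.0%, 3.5 to 6.9

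**3. What it cannot see.** Hold 25 changes in 504 fixed and vary how many were right (r) and wrong (w). The net is (r − w)/504. Its approximate 95% CI is net ± 1.96 × √[(r + w) − (r − w)²/504]/504. For 13/12 the half-width is 1.96 × √(25 − 1/504)/504 = 1.9 points; for 25/0 it is 1.96 × √(25 − 625/504)/504 = 1.9 points. The p-value is the exact two-sided sign test on the 25 changes.

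| Right / wrong | Planned statistic (95% CI) | Net, points (approx. 95% CI) | Sign test p |
|---|---|---|---|
| 25 / 0 | 5.0% (3.2 to 7.2) | +5.0 (3.1 to 6.9) | <0.0001 |
| 13 / 12 | 5.0% (3.2 to 7.2) | +0.2 (−1.7 to 2.1) | 1.0 |
| 0 / 25 | 5.0% (3.2 to 7.2) | −5.0 (−6.9 to −3.1) | <0.0001 |

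The second column never moves. The arithmetic is the same with improved and worsened in place of right and wrong. At an assumed 25% changed (126/504) the planned statistic is 25.0% (21.3 to 29.0), while the net can lie anywhere from −25.0 to +25.0 points.

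**4. The claim to detect changes.** Detection needs a null value, and none is given for prognosis. Zero does not serve: with one change in 504 the exact lower limit is 1 − 0.975^(1/504) = 0.00005, or 0.005%, already above zero. What the sample does provide is precision, namely the intervals in step 2.

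**5. Comparison with the other outcomes.** Confidence and management have paired tests that respond to direction. Diagnosis is judged against the reference. Management also has a reference-linked measure in the health economics section (Section 4), which counts decisions appropriately revised. Prognosis has neither feature.

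**The case against.** A reader might infer that the plan would declare MR effective even if it carried no information or mostly misled. The documents do not support that. The prognosis percentage has no test, null value or success threshold, and nothing rests the secondary hypothesis on it alone. A misleading MR would be expected to show in the primary paired accuracy comparison, in the events of Section 8 Table 2 (MR disagreeing with the reference), and in the economic measures of appropriately revised decisions and correctly revised diagnoses. Nor can it be said how much of the percentage would be re-rating noise: no re-rating figure is given, and the feedback form is meant to record what MR changed, so it is not a blind second rating.

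Frequency of revision is also a legitimate description of influence on counselling, and a table by direction may well be in the unseen SAP. Both points stand. They are why the percentage should be kept, and why the point concerns what the Protocol fixes as the effect measure.

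A further temptation is to replace the percentage with a net figure, changes where MR was right minus changes where ultrasound was right, and rest the hypothesis on it. That goes too far. The reference is anatomical, whereas the scale expresses the chance of normal neurodevelopment. A correct anatomical diagnosis can be followed by a misdirected prognosis, and the net figure would itself ignore direction.

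Finally, Project 2 of the 2-3 year follow-up protocol does compare ultrasound and MR prognosis with developmental outcome. It is a separate, later study and leaves this outcome unchanged.

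What remains is that the safeguards address diagnosis and management; within the main study none shows whether the revised prognoses were supported.

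**Conclusion.** The point holds as a limit on what the prognosis outcome can show. As fixed in Section 9 it estimates how often the category was revised after MR, and at the plan's own 5% it reads 5.0% (3.2 to 7.2) for helpful, chance and misleading revisions alike. This follows from the form of the statistic and needs no assumption about re-rating; only the illustrative splits are assumed. The 504 denominator is the plan's expected number of completed cases.

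The consequence is moderate. This is a secondary outcome without a decision rule, and the primary result is unaffected. The wording on detecting changes has no clear meaning for prognosis, although it does for management, which is tested.

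**What to change.** In Section 9 (Secondary Analyses):
- Keep the overall percentage changed, with its interval, as description.
- Add the 4x4 before/after table, the percentages improved and worsened, their paired difference with a 95% CI, and a signed-rank or marginal-homogeneity test. State that direction alone is not correctness: a worsened prognosis may be the right one.
- Among cases with a reference diagnosis, tabulate changes by direction and by panel verdict (MR right and ultrasound wrong, MR wrong and ultrasound right, both right, both wrong). Label this supportive, and say that anatomical agreement is only a proxy for prognostic correctness.
- State that the gross percentage alone will not be cited as evidence of a clinically effective contribution.

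In Section 9 (Sample size), restate the claim for prognosis as precision: about 3.2 to 7.2% if 5% of 504 cases change.

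**Cost.** No new data: the referral form, the feedback form and the panel verdict supply everything. It takes one extra cross-tabulation and some wording. The supportive part covers only cases with a reference diagnosis, about 504 of 750, and at 5% changed its cells would be small (about 25 changes spread over two directions and four verdicts), so it should be read descriptively.
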